9.1.4. Subject Death

In this registry, death is not considered an AE, but rather the outcome of an AE. An ongoing AE at the time of death or registry withdrawal will remain categorized as ongoing.

Attempts will be made by the Site to obtain death certificate and autopsy reports, when possible.

9.2. Unanticipated Serious Adverse Device Effects (USADE)

The sponsor is required to notify the appropriate regulatory agencies per local requirements of any USADE. Therefore, if a complication occurs that the investigator believes may be a potential USADE, the site should immediately contact the sponsor and EC to determine reporting requirements.

9.3. Device Deficiency

Device deficiencies are defined as Any inadequacy in the identity, quality, durability, reliability, safety, or performance of an investigational device, including malfunction, use errors, or inadequacy in information supplied by the manufacturer. All device deficiencies – even those that could have led to a SAE should be reported to the Sponsor immediately.

The following information on each reported deficiency will be collected:

- Description of deficiency
- Date of occurrence
- Batch code and lot number of the affected device
- Related subject, user or other persons AE information (if applicable)

Due to the retrospective approach, any device deficiency may have already been reported as part of the hospital's routine via Product Surveillance Group procedures. To close any potential gaps, sites are asked to report all device deficiency in the EDC.

CONFIDENTIAL INFORMATION

9.4. Clinical Event Committee

An independent Clinical Events Committee (CEC) will review endpoint related clinical events during the registry to ensure the consistency of endpoints reported by the site. The █ 21-04 CEC will be comprised of an interdisciplinary team of three members with pertinent expertise who are not directly involved in the conduct of the registry.

CEC will be managed by █ to ensure the independency of the members from the sponsor.

Sponsor will not take part of any CEC activities and may only deliver initial training to the CEC members on the protocol and registry device.

After review, the CEC will inform █ whether or not additional data is required to evaluate any specific event, whether or not clarifications are needed.

Site may need to send anonymized source documentation to CRO related to the events that need to be adjudicated by CEC.

This committee will operate under pre-specified procedures as outlined in its charter. The frequency of data review and other roles and responsibilities of the committee will be specified in the registry specific CEC charter.

10. Statistical Analysis

10.1. Registry Hypotheses

The registry is designed to statistically test the hypothesis that the Target Vessel Patency at 12 months (Primary Performance Endpoint) in both FEVAR and BEVAR populations of subjects is greater than 77%. The hypothesis will be tested separately in the two cohorts (FEVAR and BEVAR), using the subjects with imaging results available for the 12 months visit. The binomial exact test will be used with a one-sided 2.5% level of significance to test the null hypothesis.

The statistical hypothesis is specified as follows:

$H_0: P < 77\%$

$H_A: P \geq 77\%$

Alpha= 0.025 (one-sided)

Whereas P is the probability of maintaining Target Vessel Patency at 12 months.

The ITT population will be used to perform this test.

A separate analysis in the subgroup with mixed placement of branched and fenestrated endografts as well as other clinical uses not described as only FEVAR or BEVAR will also be assessed with no formal hypothesis.

10.2. Sample Size Assumptions

The assumptions used for the calculation of sample size in the registry included the anticipated performance of the █ for the FEVAR and BEVAR procedures, the acceptance criteria determined from the █. The preliminary clinical evaluation suggested that the █

in the FEVAR and BEVAR cohorts respectively.

CONFIDENTIAL INFORMATION

10.3. Sample Size Determination

Using the above assumptions, the [REDACTED]

[REDACTED] enrolled in the FEVAR and BEVAR cohorts respectively.

10.4. Data Analysis

10.4.1. Timing of Analyses

The analysis to test the primary hypothesis will be conducted once all subjects have completed their 12 Month follow-up, data has been entered and cleaned in the EDC system. Subjects with a visit within 90 days of the annual time frames will be considered for analysis of the annual outcomes. [REDACTED]

[REDACTED]. The subject follow-up will continue for five years, and the final analysis will be done once all subjects have completed five-year follow-up. Separate analysis will be performed for FEVAR and BEVAR cohorts. No interim analysis for the early termination of registry is planned due to the post marketing usage of the [REDACTED] and retrospective nature of the enrollment. In addition, once the primary analysis has been performed and hypothesis tested, further analyses may also be performed as needed for annual reports, presentations and publications based on interim data or at any other time at the discretion of Gore.

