3.4.3. Secondary Endpoints

Secondary performance outcomes

- Reintervention (total and reintervention that can be attributed to branches originally treated with the [REDACTED]) at 12 months and annually through 5 years post-implant
- Target Vessel Technical Success
- Primary Technical Success (Total Endovascular Procedure)
- Target vessel instability at 12 months and annually through 5 years post-implant
- Target vessel patency, patient level, annually from 2-5 years post-implant (extended primary endpoint)
- Target vessel patency, vessel level analysis, annually from procedure to 5 years post-implant

Secondary safety outcomes

- Aneurysm-related mortality at 12 months and annually through 5 years post-implant
- MAEs at 30 days

CONFIDENTIAL INFORMATION

4. Registry Population

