10.4.6. Statistical Analysis of Secondary Endpoint(s)

Tables of each secondary endpoint will be [REDACTED] [REDACTED] Missing data at the time of analysis will not be imputed.

11. Ethical and Regulatory Considerations

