5.0 Statistical Analyses

[figure not shown]
Analysis Populations

- The registry population will consist of patients that have had treatment with GORE® [REDACTED]® [REDACTED] and that meet the registry eligibility criteria.

CONFIDENTIAL INFORMATION

Page 10 of 15

Timing of Analyses

The analysis to test the primary hypothesis will be conducted once all subjects have completed their 12 Month follow-up, data has been entered and cleaned in the EDC system. Subjects with a visit within 90 days of the annual time frames (i.e., 275 – 455 for 12 Month visit) would be considered for analysis of the annual outcomes. In case of the multiple visits within the interval, the visit closest to and preceding the annual time point would be considered for the determination of the outcomes.

[REDACTED]
The subject follow-up will continue for five years, and the final analysis will be done once all subjects have completed five-year follow-up. [REDACTED]

[REDACTED] No interim analysis for the early termination of registry is planned due to the post marketing usage of the [REDACTED] Stent Graft and retrospective nature of the enrollment. In addition, once the primary analysis has been performed and hypothesis tested, further analyses may also be performed as needed for annual reports, presentations and publications based on interim data or at any other time at the discretion of Gore.

CONFIDENTIAL INFORMATION

Page 11 of 15

Analysis Populations

Intent-to-Treat (ITT) dataset will consist of all enrolled patients meeting the inclusion / exclusion criteria and treated at least one vessel with the [REDACTED] Stent Graft. A subset of the ITT dataset will be further identified of subjects with all vessels treated with [REDACTED] and another subset with all vessels treated with [REDACTED] only. ITT dataset will be used for the analysis of the primary and secondary endpoints. Similarly, per vessel analysis will be performed with all three datasets after identifying each vessel treated by [REDACTED] and also of the vessels treated without [REDACTED]

[REDACTED]

Pooling of Data

All sites in the registry will follow a common protocol and the data will be monitored to assure compliance. The data collection and handling procedures will be the same at all registry Sites. As such, there is no concern in pooling data from different sites together for analysis.

[REDACTED]

Statistical Analysis of Primary Endpoint(s)

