Analysis of the Primary Endpoint to test the hypothesis will be performed using binomial exact test using one-sided 2.5% level of significance.

All subjects with follow-up visit and imaging results available from 9 to 15 months will be included in the primary analysis. Subjects with the loss of Target Vessel Patency earlier than 15 months will also be included in such analysis and considered as failures regardless of the timing and availability of another visit between 9 to 15 months.

[REDACTED]

Statistical Analysis of Secondary Endpoint(s)

[REDACTED]

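### The ±90-day visit rule is not limited to imaging outcomes; applied as written, it would drop every death before day 275 from annual aneurysm-related mortality

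*Protocol*

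**What the plan says.** **The visit rule.** Protocol 10.4.1 reads: "Subjects with a visit within 90 days of the annual time frames will be considered for analysis of the annual outcomes". SAP 5.0, under Timing of Analyses, has the same rule with days added: "Subjects with a visit within 90 days of the annual time frames (i.e., 275 – 455 for 12 Month visit". Such subjects "would be considered for analysis of the annual outcomes". If several visits fall in the window, the SAP picks one of them to determine the outcome. No readable words limit either sentence to imaging or to patency.

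**The outcomes called annual.** Protocol 3.4.3 and SAP 2.3 list "Aneurysm-related mortality at 12 months and annually through 5 years post-implant" and "Target vessel instability at 12 months and annually through 5 years post-implant". Reintervention is likewise set "at 12 months and annually through 5 years post-implant". Under the definitions in Protocol 3.4.1, aneurysm-related mortality includes every death in the first 30 days, and target vessel instability includes death from a side-branch complication.

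**The exception.** In the SAP 5.0 text on the primary endpoint, subjects who lose target vessel patency before 15 months are included and "considered as failures regardless of the timing and availability of another visit between 9 to 15 months". This is worded for patency loss in that analysis.

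**The rest.** Both documents use the ITT set for secondary endpoints. The secondary-endpoint methods are blacked out in Protocol 10.4.6 and SAP 5.0, as is some text following the visit rule. In 10.4.6 the readable remainder includes "Missing data at the time of analysis will not be imputed".

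**The concern.** Patency status is read at a visit, so a visit window suits it. Aneurysm-related mortality, target vessel instability and reintervention are events that accumulate from the index procedure. For a fatal event, the event itself prevents the later visit. If a window visit is the condition for entry, early deaths leave both numerator and denominator.

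The SAP deals with this for patency, where early losses count without a window visit. No readable text does the same for the other annual outcomes.

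The secondary objective is to confirm safety. Aneurysm-related mortality is one of two listed safety outcomes and the only one that extends past day 30.

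**Working it through.** **1. The plan's own figure.** 365 − 90 = 275 and 365 + 90 = 455, which matches the SAP. Nine to 15 months at 30.4375 days per month is day 273.9 to 456.6, which agrees with the window in the primary analysis. The 24-month window opens on day 730 − 90 = 640.

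**2. Who can meet the condition.**

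| Event | Window visit possible afterwards? | Readable exception? |
|---|---|---|
| Loss of patency before the window | Yes, if alive | Yes, in the primary analysis |
| Death within 30 days | Never, at any annual time point | No |
| Aneurysm-related death after day 30, before day 275 | Never | No |
| Branch-related death before day 275 | Never | No |
| Non-fatal instability event or reintervention | Yes, if the patient attends | No |

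On this reading the 30-day part of the mortality definition could not contribute to any annual estimate. A cumulative count could also fall over time: a patient seen early in the 12-month window who dies before day 365 counts at month 12 but cannot have a visit from day 640 on.

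**3. Size for aneurysm-related mortality (illustration).** The documents give no rates, so all three inputs are assumptions:
- e, the share dying of an aneurysm-related cause before day 275: 2%, 5% or 8%.
- l, the share dying of such a cause after a window visit but by day 365: 0.5%.
- m, the share of other patients without a window visit: 0%, 10% or 20%.

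With all ITT patients in the denominator and every event counted, the 12-month figure is e + l. Under the rule as written it is l / (1 − e − m). For e = 5% and m = 10% this is 0.005 / 0.85 = 0.59%. Cohort size (100 or 120) cancels.

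| e | All events counted | As written, m = 0% | m = 10% | m = 20% |
|---|---|---|---|---|
| 2% | 2.5% | 0.51% | 0.57% | 0.64% |
| 5% | 5.5% | 0.53% | 0.59% | 0.67% |
| 8% | 8.5% | 0.54% | 0.61% | 0.69% |

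The figure under the rule hardly changes with the early death rate.

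**4. Target vessel instability (illustration).** Assume 5 early deaths, all branch-related, an event in 10% of the remaining patients, and attendance unrelated to events among survivors.
- N = 100: (5 + 0.10 × 95) / 100 = 14.5%, against 10.0% as written.
- N = 120: (5 + 0.10 × 115) / 120 = 13.8%, against 10.0% as written.

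**5. Non-fatal events.** Let q be the true proportion with an event, a1 the window attendance of patients with an event and a0 that of patients without. The rule reports q·a1 / (q·a1 + (1 − q)·a0). With q = 10% assumed:
- a1 = a0 gives 10%.
- a1 = 70%, a0 = 90% gives 0.07 / (0.07 + 0.81) = 8.0%.
- a1 = 90%, a0 = 70% gives 0.09 / (0.09 + 0.63) = 12.5%.

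The direction depends on who attends, and the documents say nothing about that.

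**The case against.** The other side has a strong case.

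- **Redaction.** The places where a counting rule for secondary outcomes would stand are blacked out, and blacked-out text is not absent from the plan. This stands, and it makes the point conditional.
- **Wording.** The sentence says who will be considered, without the word only. The protocol's modification summary calls the addition a clarification of visit windows, so it may be no more than a rule for assigning visits to time points. That is possible. But the SAP's patency exception is needed only if the window otherwise acts as an entry condition.
- **ITT, and retention of patients who die.** Secondary endpoints use the ITT set. Protocol 4.1 keeps patients who die in the registry, and 3.3 treats exclusion of deceased patients at enrolment as a serious source of bias. These show intent but do not override the rule. The primary test is also labelled ITT, yet Protocol 10.1 and SAP 2.4 restrict it to subjects with 12-month imaging.
- **No imputation.** A recorded death is not missing data, so 10.4.6 does not itself remove it. This stands; the difficulty lies in the visit rule alone.
- **The other safety outcome.** All-cause mortality is a component of MAEs at 30 days, which is not an annual outcome. Deaths in the first 30 days would still be reported there. This stands and limits the effect on safety reporting.
- **Non-fatal events.** A living patient with an early reintervention can still attend in the window. This stands, as step 5 shows.

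**Conclusion.** The point holds as a conditional one. As readable, the visit rule covers all annual outcomes, and the only early-event exception is for patency. Applied as written, it removes every death before day 275 from annual aneurysm-related mortality and every such branch-related death from target vessel instability. For fatal events the bias is favourable. Non-fatal instability events and reinterventions in patients without a window visit also go uncounted, with the direction of bias unknown.

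Under the assumed rates, 12-month aneurysm-related mortality of 2.5% to 8.5% would appear as 0.5% to 0.7%. These figures show the mechanism and are not forecasts.

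Two stronger readings are tempting. A reader might infer that these patients are in fact left out and that safety will be judged on survivors. The documents do not support this: the secondary methods cannot be read and may count events from day 0, and 30-day deaths are reported elsewhere. A reader might also infer that all three outcomes are biased favourably. That follows only for fatal events.

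The primary test has its own exception and is not affected. These are secondary outcomes with no readable hypothesis test, so the point calls for a correction of wording and ranks below a must-fix.

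**What to change.** In Protocol 10.4.1 and SAP 5.0, limit the ±90-day visit rule to outcomes read from imaging at a visit, that is, patency status.

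For aneurysm-related mortality, target vessel instability and reintervention, state that all adjudicated events from the index procedure count, with or without a window visit. Estimate cumulative incidence from day 0 in the ITT set, separately for FEVAR and BEVAR. Censor at last contact and treat deaths that are not themselves the event as competing events. Avoid a simple proportion that sets all events against only those patients documented event-free at the time point; it drops event-free patients lost to follow-up and inflates the rate.

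If the redacted text already does this, a cross-reference in the visit rule is enough.

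The cost is wording. The readable protocol already asks for reintervention dates (5.10), adverse events from the index procedure with onset date and outcome (9.1.3), and committee review of endpoint events (9.4). The sponsor should confirm that dates of death and of last contact are in the analysis data. The downside is that reported rates may become less favourable.

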10.4.2. Analysis Populations

Intent-to-Treat (ITT) dataset will consist of all enrolled patients meeting the inclusion / exclusion criteria and treated at least one vessel with the [REDACTED]. [REDACTED] ITT dataset will be used for the analysis of the primary and secondary endpoints. In addition, Per-Protocol dataset will also be created after excluding subjects not meeting inclusion/exclusion criteria or the vessels treated with the devices other than the [REDACTED]. Similarly, per vessel analysis will be performed with both datasets after identifying each vessel treated. Per vessel analysis will be further identified by type of main body portal and vessel treated e.g., BEVAR SMA, BEVAR Celiac, Fenestrated renal, BEVAR renal etc. and may include vessels from the cohort of subjects treated with mixed FEVAR/BEVAR procedures.

10.4.3. Registry Deviations

The registry protocol deviations will be assessed descriptively and their potential impact on the registry results will be evaluated considering the nature of such deviations. The sample size for the registry is increased by 10% to compensate for the missed visits to that extent and allow for the testing of the registry hypothesis without compromising the power.

CONFIDENTIAL INFORMATION

10.4.4. Pooling of Data

All sites in the registry will follow a common protocol and the data will be monitored to assure compliance. The data collection and handling procedures will be the same at all registry Sites. As such, there is no concern in pooling data from different sites together for analysis. Gore may perform analyses to explore differences in device performance by gender, age, or any other subgroup of interest.

10.4.5. Statistical Analysis of Primary Endpoint(s)

Analysis of the Primary Endpoint to test the hypothesis will be performed using [REDACTED] [REDACTED]. Missing data at the time of analysis will not be imputed.

10.4.6. Statistical Analysis of Secondary Endpoint(s)

Tables of each secondary endpoint will be [REDACTED] [REDACTED] Missing data at the time of analysis will not be imputed.

11. Ethical and Regulatory Considerations

11.1. Statement of Compliance

The requirements of Clinical Investigation of Medical Devices for Human Subjects Good Clinical Practice (ISO14155-2020), International Conference on Harmonization Good Clinical Practice (ICH E6 (R2), have been incorporated into applicable Clinical Quality System procedures.

The following are applicable to this registry:

ICH-GCP E6 (R2)	International Conference on Harmonization Regulations Guideline For Good Clinical Practice
Regulation (EU) 2017/745	Regulation (EU) 2017/745 of the European Parliament and of the Council on medical devices,
ISO 14155:2020(E)	Clinical investigation of medical devices for human subjects – Good clinical practice

11.2. Compliance Responsibilities

The sponsor will conduct the registry in accordance with all applicable regulations and laws. The sponsor will be responsible for documenting that investigators have the necessary skills, training, and information to properly conduct the registry. The sponsor will confirm proper monitoring of the registry and verify that the site has obtained EC approval prior to enrollment. The sponsor will provide information to the investigators, the reviewing EC concerning the progress of and any new material information about the registry.

CONFIDENTIAL INFORMATION

The investigator will conduct the registry in accordance with all applicable regulations and laws, any relevant agreements, the registry protocol, and all approval conditions of the reviewing EC. Any additional requirements imposed by the EC shall be followed. The investigator will verify EC approval is obtained prior to enrollment, maintained throughout the course of the registry, and that all EC reporting requirements are met. The investigator is responsible for protecting the rights, safety, and welfare of subjects under the investigator's care. The investigator is also responsible for ensuring that informed consent is properly obtained or a possible waiver documented as required.

The investigator will determine the cause and implement appropriate corrective and preventive actions to address significant noncompliance.

The registry shall be conducted in accordance with the ethical principles that have their origin in the Declaration of Helsinki.

11.3. Informed Consent

The investigator shall verify that all potential subjects still alive and reachable for this registry are provided with an EC approved consent form describing this registry and sufficient information to make an informed decision about their participation. In case of deceased patients, the next of kin/legal representative could sign the informed consent form unless a waiver has been granted by the EC.

The formal consent of a subject, using the EC-approved consent form, must be obtained by the investigator or designee before that subject undergoes any registry-related follow-up procedure. The consent form will be signed and personally dated by the subject and the person who conducted the informed consent discussion. Next of kin/legal representative can sign on behalf of the subject if he/she is unable to make the decision to participate or if subject deceased at registry entry, (unless a waiver was granted), according to local regulations.

The original signed informed consent form will be retained in the subject records. A copy of the informed consent document will be given to the subject for his or her records. Any significant, new information which emerges while the registry is in progress that may influence a subject's willingness to continue to take part in the registry will be provided to the subject or LAR.

The investigator or designee shall verify that documentation of the acquisition of informed consent is recorded in each subject's records in accordance with applicable regulations.

Emergency contact details for reporting serious adverse events and serious adverse device effects will be listed in the EC-approved Informed Consent Form.

